7.2 Withdrawal from the study

A patient may withdraw from the study (eg, withdraw consent), at any time (investigational product and assessments) at his/her own request, without prejudice to further treatment.

A patient who considers withdrawing from the study must be informed by the Investigator that the day of withdrawal will be considered as the end of study phase for the patient. However, the patient will still have the provision of spontaneous AE reporting.

If the patient withdraws consent for disclosure of future information, the sponsor may retain and continue to use any data collected before such a withdrawal of consent.

If a patient withdraws from the study, he/she may request destruction of any samples taken, and the investigator must document this in the site study records.

A patient who withdraws consent will always be asked about the reason(s) and the presence of any adverse events (AE). The Investigator will follow up patients as medically indicated.

AstraZeneca or its delegate will request investigators to collect information on patients' vital status (dead or alive; date of death when applicable) at the end of the study from publicly available sources, in accordance with local regulations. Knowledge of the vital status at study end in all patient is crucial for the integrity of the study.

See SoA, Table 1, for data to be collected at the time of study discontinuation and follow-up and for any further evaluations that need to be completed.

8. STUDY ASSESSMENTS AND PROCEDURES

Study procedures and their timing are summarised in the SoA.

The investigator will ensure that data are recorded on the paper or electronic Case Report Forms.

The investigator ensures the accuracy, completeness for CRFs (electronic or paper) include: legibility and timeliness of the data recorded and of the provision of answers to data queries according to the Clinical Study Agreement. The investigator will sign the completed paper/electronic Case Report Forms. A copy of the completed paper/electronic Case Report Forms will be archived at the study site.

Immediate safety concerns should be discussed with the sponsor immediately upon occurrence or awareness to determine if the patient should continue or discontinue Study treatment.

Adherence to the study design requirements, including those specified in the SoA, is essential and required for study conduct.

All screening evaluations must be completed and reviewed to confirm that potential patients meet all eligibility criteria. The investigator will maintain a screening log to record details of all patients screened and to confirm eligibility or record reasons for screening failure, as applicable.

Procedures conducted as part of the patient's routine clinical management (eg, blood count) and obtained before signing of the ICF may be utilised for screening or baseline purposes provided

AstraZeneca

the procedures met the protocol-specified criteria and were performed within the time frame defined in the SoA.

The maximum amount of blood collected from each patient will not exceed approximately 10 mL/visit. Repeat or unscheduled samples may be taken for safety reasons or for technical issues with the samples.

8.1 Efficacy assessments

8.1.1 Clinical safety laboratory assessments

See Table 6 & 7 for the list of clinical safety laboratory tests to be performed and to the SoA for the timing and frequency. All protocol-required laboratory assessments, as defined in the table, must be conducted in accordance with the laboratory manual and the SoA.

The Investigator should make an assessment of the available results with regard to clinically relevant abnormalities. The laboratory results should be signed and dated and retained at centre as source data for laboratory variables.

For information on how AEs based on laboratory tests should be recorded and reported, see Section 8.2.6.

Additional safety samples may be collected if clinically indicated at the discretion of the Investigator. The date, time of collection and results (values, units and reference ranges) will be recorded on the appropriate CRF.

The clinical chemistry, haematology and urinalysis will be performed at a local laboratory at or near to the Investigator site. Sample tubes and sample sizes may vary depending on laboratory method used and routine practice at the site.

Table: 5 Haematology

Haematocrit

Haemoglobin

Basophils

Eosinophils

Monocytes

Absolute Neutrophil Count

Platelet count

Total Lymphocyte count including differential

Table: 6 Clinical chemistry (serum or plasma)

Albumin

Glucose

Alkaline phosphatase^a

Lactate dehydrogenase

Alanine aminotransferase^a

Lipase^b

Aspartate aminotransferase^a

Magnesium^b

Amylase^b

Potassium

Bicarbonate

Sodium

Calcium

Total bilirubin^a

Chloride

Total protein

Creatinine (creatinine clearance)^b

Urea or blood urea nitrogen, depending on local practice

Gamma glutamyltransferase

Uric acid^b

TSH

Urine Routine and microscopy

- a Tests for aspartate aminotransferase, alanine aminotransferase, alkaline phosphatase, and total bilirubin must be conducted concurrently and assessed concurrently.
- b Creatinine clearance, magnesium, amylase, lipase, and uric acid tested at Screening Day 1 (unless screening laboratory assessments are performed within 3 days prior to Day 1) and every 4 weeks thereafter.
- c Gamma glutamyltransferase tested at Screening, Day 1 and as clinically indicated. Clinical chemistry assessments to be performed at each visit and when clinically indicated.
- **NB.** All patients with an AST, ALT or bilirubin value (the latter ≥ 1.5 x ULN) at the time of the last dose of study drug should have a further liver chemistry profile (AST, ALT, bilirubin and alkaline phosphatase) performed 30 days (± 7 days) after permanent discontinuation of study drug.

Haematology and clinical chemistry tests will be performed by the hospital's local laboratory. Additional analyses may be performed if clinically indicated.

Any clinically significant abnormal laboratory values should be repeated as clinically indicated and recorded on the eCRF. See Section 6.4.3 for when abnormal laboratory values should be reported as AEs.

All patients who have any Common Toxicity Criteria (CTC) Grade 3 or 4 laboratory values at the time of completion or discontinuation from study drug must have further tests performed

until the laboratory values have returned to CTC Grade 1 or 2, unless these values are not likely to improve because of the underlying disease.

8.1.2 Physical examinations

For timing of individual measurements refer to the study schedules (Table 1 [Screening and the Treatment Period]

A complete physical examination will be performed and will include an assessment of the following (as clinically indicated): general appearance, respiratory, cardiovascular, abdomen, skin, head and neck (including ears, eyes, nose and throat), lymph nodes, thyroid, musculo-skeletal (including spine and extremities), genital/rectal and neurological systems.

Performance status will be assessed using WHO performance status.

8.1.3 Vital signs

- For timings of assessments refer to the study plans in Table 1 (Screening and the Treatment Period).
- Patients will be monitored with assessment of vital signs (BP, pulse, respiratory rate, temperature and oxygen saturation) at Screening and on the day of each infusion and in the follow-up period. On infusion days vital signs will all be taken before the infusion.
- Additional monitoring with assessment of vital signs is at the discretion of the Investigator per standard clinical practice or as clinically indicated.
- Additional recording of vital signs may be captured on an unscheduled vital signs eCRF and on the eCRF for AE/SAE where applicable. The date and time of collection and measurement will be recorded on the appropriate eCRF.
- The date and time of collection and measurement will be recorded on the appropriate eCRF.
- Temperature, respiratory rate and oxygen saturation: On infusion days, temperature, respiratory rate and oxygen saturation should be collected before the infusion.

8.1.4 Electrocardiograms

Clinical interpretation and management of patients for all ECGs will be done locally. The same method of assessment should be used throughout. Electrocardiograms will be recorded at 25 mm/sec. Resting 12-lead ECGs will be recorded at screening and as clinically indicated throughout the study. ECGs should be obtained after the patient has been rested in a supine position for at least 5 minutes and recorded while the patient remains in that position. In case of clinically significant ECG abnormalities, including a QTc value >470 ms, 2 additional 12-lead ECGs should be obtained over a brief period (eg, 30 minutes) to confirm the finding.

All ECGs should be assessed by the Investigator as to whether they are clinically significantly abnormal / not clinically significantly abnormal. If there is a clinically

significant abnormal finding, the Investigator will record it as an AE on the eCRF (see Section 6.4.3).

At Screening, mean QTc with Bazett's correction (QTc = QT/ \sqrt{R}) must be <470 msec.

8.1.5 Weight

Weight of the patient will be measurement at alternate visits .Dose calculation will be as per weight of the patient.

8.2 Collection of adverse events

The Principal Investigator is responsible for ensuring that all staff involved in the study are familiar with the content of this section

The definitions of an AE or SAE can be found in Appendix B.

AE will be reported by the patient (or, when appropriate, by a caregiver, surrogate, or the patient's legally authorized representative).

The investigator and any designees are responsible for detecting, documenting, and recording events that meet the definition of an AE or SAE. For information on how to follow/up AEs see section 8.3.3.

8.2.1 Method of detecting AEs and SAEs

Care will be taken not to introduce bias when detecting AEs and/or SAEs. Open-ended and non-leading verbal questioning of the patient is the preferred method to inquire about AE occurrences.

8.2.2 Time period and frequency for collecting AE and SAE information

Adverse events and SAEs will be collected from time of signature of informed consent, throughout the treatment period (20 weeks) and including the follow-up period (90 days after the last dose of study drug) in patients who discontinue before 20 weeks.

If a patient discontinues from study drug for reasons other than disease progression, drug-related SAEs must be captured until the patient is initiated on an alternate intervention or upto 90 days whichever is earlier.

All SAEs will be recorded and reported to the sponsor or designee within 24 hours, as indicated in Appendix B. The investigator will submit any updated SAE data to the sponsor within 24 hours of it being available.

Investigators are not obligated to actively seek AE or SAE in former study patients. However, if the investigator learns of any SAE, including a death, at any time after a patient's last visit and he/she considers the event to be reasonably related to the Study treatment or study participation, the investigator may notify the sponsor.

The method of recording, evaluating, and assessing causality of AE and SAE and the procedures for completing and transmitting SAE reports are provided in Appendix B.

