This is a Phase IV, open-label, single arm, multi-center, prospective study to be conducted in India. Two cohorts of patients will be included in the current study patients with locally advanced, unresectable NSCLC whose disease has not progressed following platinum-based chemoradiation therapy (N= 100). Potential patients will undergo eligibility determination within 7 days prior to first dose. Patients who meet the protocol-defined inclusion/exclusion criteria will be prospectively enrolled in a sequential manner at 10 centres in India. All enrolled patients will be treated with durvalumab administered intravenously over 60 minutes at 10 mg/kg every 2 weeks. The treatment period for this study is 20 weeks, which corresponds to 10 doses of study drug administration. Treatment will continue as long as clinical benefit is observed for a maximum of 20 weeks or either of the criteria defined in section 7 are met, whichever is earlier. Patients who are observed to continue to receive clinical benefit from durvalumab at end of Week 20 (as defined in SoA) will continue treatment in post-trial phase (defined in section 6.7). Any patient who discontinues treatment with durvalumab before end of Week 20 on study will be followed for 90 days after discontinuation of study drug or until the start of alternate treatment intervention, whichever is earlier.

Safety will be evaluated throughout the evaluation phase and during the follow up of patients who discontinue treatment before end of Week 20 by physical exams including vital signs, AE/SAE monitoring, laboratory evaluations and recording of concomitant medications.

Screening Phase (Visit 1)

Patients, or their legally acceptable representative, will provide written informed consent before any trial-specific procedures are performed. During the Screening Phase, eligibility criteria will be reviewed and a complete clinical evaluation will be performed as specified in the Time and Event Schedule. Screening procedures will be performed 7 days before first dose (week 0, day 1). All baseline disease characteristics will be captured based evaluation performed as a part of routine clinical practice. The documented tests that are required before consideration of patient for durvalumab treatment based on the local prescribing information by investigator must have been performed 28 days before first dose (week 0, Day 1).

Evaluation Phase (Visit 2 To 11)

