The Evaluation Phase will extend from first dose (Week 0, Day 1) to end of Week 20; or until study drug discontinuation due to either disease progression or unacceptable toxicity; or other reasons whichever occurs first, as listed in Section 7. Details of the procedures performed during the Evaluation Phase are outlined in the Time and Events Schedules. Patients will be closely monitored for adverse events and other safety evaluations including laboratory investigations, concomitant medications. If disease progression is diagnosed before end of week 20 then the patient will discontinue study drug with completion of the End-of-Evaluation Visits on the day of progression, and will enter the safety Follow-up Phase.

End-Of- Evaluation Visit (EoE)

An End-of- Evaluation Visit is to be scheduled on end of week 20 (Day 141) of the study. In a case where patient discontinues the study treatment for any reason listed in Section 7.1 before 20

Drug Substance - DURVALUMAB Study Code - D133HC00003 Version 4.1, Date: 12 October 2022

weeks, last visit of the patient will be considered as End-of- Evaluation visit. Every effort should be made to conduct the telephonic End-of-Study Visit before the patient starts subsequent treatment.

Follow Up Phase (End-Of-Study)

A telephonic follow-up will be conducted 90 days after the EOE Visit. This will be considered as End-of-Study visit.

The observation period including the Evaluation Phase and safety Follow-up phase will be up to a maximum duration of approximately 230days for each patient.

PATIENT POPULATION

Inclusion criteria

Patients are eligible to be included in the study only if all of the following inclusion criteria and none of the exclusion criteria apply:

- 1. Provision of signed, written and dated informed consent prior to any study specific Procedures
- 2. Male or female aged 18 years or older
- 3. As per local prescribing information and in view of positive benefit-risk assessment, patient prescribed Durvalumab treatment as per independent clinical judgment of treating physician for either treatment for locally advanced, unresectable non-small cell lung carcinoma whose disease has not progressed following platinum-based chemoradiation therapy (N= 100)

The ICF process is described in Appendix A 3.

Exclusion criteria

- 1. Concurrent enrolment in another clinical study, unless it is an observational (non-interventional) clinical study or the follow-up period of an interventional study

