Data will be summarized using descriptive statistics. Continuous variables will be summarized using the number of observations, mean, SD, median, and range as appropriate. Categorical values will be summarized using the number of observations and percentages as appropriate.

The safety analysis population will include all patients who sign the ICF and receive at least one dose of durvalumab.

Adverse Events (both in terms of MedDRA preferred terms and CTCAE grade) will be listed individually by patient. Any AE occurring before treatment with durvalumab will be included in the data listings but will not be included in the summary tables of AEs.

[figure not shown]
Any AE occurring within 90 days of discontinuation of investigational product (ie, the last dose of durvalumab) will be included in the AE summaries. Any events in this period that occur after a patient has received further therapy for cancer (following discontinuation of durvalumab) will be flagged in the data listings.

The study is designed in accordance with the Health Authority requirements in India. It is intended to provide information regarding the safety profile for patients in India and will contribute additional information to the overall safety profile of durvalumab. Due to the small sample size, this study should not be directly compared to the data from any other country.

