7. DISCONTINUATION OF STUDY DRUG

7.1 Discontinuation of study treatment

Patients may be discontinued from investigational product in the following situations:

- Patient decision. The patient is at any time free to discontinue treatment, without prejudice to further treatment.
- Adverse Event, that in the opinion of the investigator or the sponsor, contraindicates further dosing
- Severe non-compliance to study protocol that, in the opinion of the investigator or sponsor, warrants withdrawal; eg, refusal to adhere to scheduled visits.
- Any AE that meets criteria for discontinuation, as defined in Appendix D
- An AE related to study drug that is ≥Grade 3, with the exception of toxicities that do not meet criteria for discontinuation as defined Section 5.2
- >Grade 3 infusion reaction
- Initiation of alternative anticancer therapy including another investigational agent
- Disease progression as per investigator's clinical and imaging assessment.
- Pregnancy or intent to become pregnant.

If the patient is discontinued from study drug, the patient will be followed up until the start of subsequent anti-cancer intervention or up to a duration of 90 days whichever is earlier.

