8.3 Safety reporting and medical management

8.3.1 Reporting of serious adverse events

All SAEs have to be reported, whether or not considered causally related to the investigational product, or to the study procedure(s). All SAEs will be recorded in the CRF.

If any SAE occurs in the course of the study, then Investigators or other site personnel inform the appropriate AstraZeneca representatives within one day i.e., immediately but **no later than 24 hours** of when he or she becomes aware of it.

The designated AstraZeneca representative works with the Investigator to ensure that all the necessary information is provided to the AstraZeneca Patient Safety data entry site within 1 calendar day of initial receipt for fatal and life threatening events and within 5 calendar days of initial receipt for all other SAEs.

For fatal or life-threatening adverse events where important or relevant information is missing, active follow-up is undertaken immediately. Investigators or other site personnel inform AstraZeneca representatives of any follow-up information on a previously reported SAE within one calendar day i.e., immediately but **no later than 24 hours** of when he or she becomes aware of it.

Once the Investigators or other site personnel indicate an AE is serious in the EDC system, an automated email alert is sent to the designated AstraZeneca representative.

If the EDC system is not available, then the Investigator or other study site staff reports a SAE to the appropriate AstraZeneca representative by telephone.

The AstraZeneca representative will advise the Investigator/study site staff how to proceed.

Investigators or other site personnel send relevant CRF modules by fax to the designated AstraZeneca representative.

For further guidance on the definition of a SAE, see Appendix B of the Clinical Study Protocol.

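### For patients who stop durvalumab before week 20, the rules for collecting adverse events conflict with each other and with the 90-day analysis window, and the SAP carries neither that window nor the new-therapy flag

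*Protocol*

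**What the plan says.** The rules for a patient who stops early are spread over several places.

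- **Protocol 8.2.2, first paragraph.** AEs and SAEs of every kind are collected from consent through treatment, "including the follow-up period (90 days after the last dose of study drug) in patients who discontinue before 20 weeks". New therapy is not mentioned.
- **Protocol 8.2.2, second paragraph.** It opens "If a patient discontinues from study drug for reasons other than disease progression" and then states that "drug-related SAEs must be captured until the patient is initiated on an alternate intervention or upto 90 days whichever is earlier".
- **Protocol 8.2.2, third paragraph, and 8.3.1.** Every SAE goes to the sponsor within 24 hours. In the words of 8.3.1, "All SAEs have to be reported, whether or not considered causally related to the investigational product".
- **Protocol Synopsis (overall design).** An early stopper "will be followed for 90 days after discontinuation of study drug or until the start of alternate treatment intervention, whichever is earlier". Protocol 2.3 is equivalent and SAP 2.2.1 repeats it.
- **Protocol 7.1.** After a list of reasons for stopping that includes progression: "the patient will be followed up until the start of subsequent anti-cancer intervention or up to a duration of 90 days whichever is earlier".
- **Protocol Synopsis (End-of-Evaluation and follow-up).** The follow-up call is set at 90 days after the End-of-Evaluation visit, but also: "Every effort should be made to conduct the telephonic End-of-Study Visit before the patient starts subsequent treatment". In Table 1 this call (Visit 13) is the only AE contact after End-of-Evaluation.
- **Protocol Synopsis (statistical analysis).** The summaries take in AEs up to 90 days after the last dose. For the listings, the text adds: "Any events in this period that occur after a patient has received further therapy for cancer (following discontinuation of durvalumab) will be flagged".
- **SAP.** Section 1 gives the SAP precedence where its analysis differs from the protocol's. The footnote to Table 14.2.1.1 defines a treatment-emergent event by its start alone (after the first dose). Listings 16.3.1.1 to 16.3.1.3 have no column for a new-therapy flag.

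**The concern.** The primary endpoint is the number and proportion of patients with AEs, SAEs, AEs of special interest and on-study death. In early stoppers, what is counted depends on which paragraph a site follows. A site working from 7.1 closes AE collection when the next therapy starts. A site working from the first paragraph of 8.2.2 carries on to 90 days. Both comply with the protocol.

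The effect is not confined to wording. Section 4.4 treats a patient as complete after the last scheduled visit, and 8.2.2 does not oblige investigators to look for events in former patients. A call brought forward to precede new therapy can therefore end active ascertainment. Section 8.2.6 ties death reporting to the protocol-defined follow-up period, so the same ambiguity reaches on-study deaths.

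The planned flag needs two things that truncated follow-up may not supply: the events themselves, and the date on which further therapy began. Table 1 schedules concomitant medication up to Visit 12 and not at the follow-up call.

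**Working it through.** **The plan's own figures.** The sample size follows from n = 1.96² × p(1 − p) / d². With p = 0.31 and d = 0.10 this gives 82.17, rounded up to 83, as stated. At n = 100 the half-width is 1.96 × √(0.31 × 0.69 / 100) = 0.091. The maximum observation period is 141 + 90 = Day 231, which matches the stated figure of about 230 days. None of these is in dispute.

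**Two test cases put through each rule.** Case A stops for progression and has a non-serious AE after new therapy starts but inside 90 days of the last dose. Case B stops for toxicity, has no new therapy, and has an unrelated SAE inside 90 days.

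| Rule | Case A | Case B |
|---|---|---|
| Protocol 8.2.2, first paragraph | collect | collect |
| Protocol 8.2.2, second paragraph | does not apply | not named |
| Protocol 8.2.2, third paragraph; 8.3.1 | do not apply | record and report |
| Synopsis overall design; 2.3; 7.1; SAP 2.2.1 | follow-up over | in follow-up |
| Synopsis statistical analysis | summarise and flag | summarise |
| SAP TEAE definition and listings | count if recorded, no flag | count if recorded |

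Case A is a direct conflict: collected under one rule, outside follow-up under another, and expected by the analysis. In Case B only the second paragraph of 8.2.2 is out of line.

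**Share of the 90 days lost.** Let t be the days from last dose to next therapy. The documents give no value, so t is assumed. Share lost = (90 − t)/90.

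- t = 14: 76/90 = 84%
- t = 28: 62/90 = 69%
- t = 45: 45/90 = 50%
- t = 60: 30/90 = 33%

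More than half is lost only if t is below 45 days.

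**Share of the whole window, first dose to 90 days after the last.** With the last dose on study day L, share lost = (90 − t)/((L − 1) + 90).

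| L (whole window) | t = 14 | t = 28 | t = 45 | t = 60 |
|---|---|---|---|---|
| Day 43 (132 days) | 58% | 47% | 34% | 23% |
| Day 85 (174 days) | 44% | 36% | 26% | 17% |
| Day 127 (216 days) | 35% | 29% | 21% | 14% |

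**Patients with a missed first AE, illustration only.** Assume that a fraction f of patients is affected, that the 90-day risk of a first AE is q, and that the hazard is constant. Missed per 100 = 100 × f × [(1 − q)^(t/90) − (1 − q)].

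- Low end, f = 0.1, q = 0.1, t = 45: 100 × 0.1 × (0.9487 − 0.9) = 0.5
- High end, f = 0.3, q = 0.3, t = 14: 100 × 0.3 × (0.9460 − 0.7) = 7.4

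**The case against.** Several points on the other side are sound.

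- **Progressors and 8.2.2.** A reader might infer from the second paragraph that progressors have their collection narrowed. It excludes them. For progressors the conflict rests on the Synopsis, 2.3 and 7.1 against the first paragraph of 8.2.2.
- **Only drug-related SAEs.** A reader might also infer that nothing else is collected from non-progressors. The paragraph says what must be captured, which can be read as a minimum, and the paragraphs either side of it and 8.3.1 are broader. The text is ambiguous; it is not a clear restriction.
- **Events never collected.** This goes too far. The first paragraph of 8.2.2 collects them, the 90-day call carries no stated cut, and the request to call before new therapy is best-effort. What stands is that collection is inconsistent, so the flag cannot be relied on.
- **Most of the window lost.** The documents do not support this. They give no time to next therapy and do not say that progressors move on quickly. Nor do the median onset times in Table 3 measure missed events: they come from a combined monotherapy database and carry no incidence.
- **Stopping at new therapy is defensible.** It limits contamination by the next drug. As a design choice that stands, but it is not the choice the Synopsis analysis makes.
- **SAP silence.** One can argue that silence leaves the protocol's window and flag in force. Even so, the SAP's definition and listings do not implement them.

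**Conclusion.** The conflict is real and affects how the primary endpoint is ascertained in patients who stop before week 20. Patients who start new therapy early can lose part of the 90-day window, and that loss tends to lower the reported incidence. Differences between sites in which rule they follow add variation that cannot be separated out afterwards.

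The size cannot be fixed from the documents. Under the assumed times to next therapy, 33% to 84% of the 90 days is lost, and 14% to 58% of the whole window; the latter passes half in one of the twelve combinations shown. The illustration of 0.5 to 7.4 missed first-AE patients per 100 rests entirely on assumed inputs and lies below the 9.1-point half-width at n = 100. The case for change rests on contradictory rules for a primary endpoint, not on a demonstrated large bias. It concerns early stoppers only.

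**What to change.** Use one window for both collection and analysis, the one the Synopsis statistical text already assumes.

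1. In every patient who stops before week 20, collect all AEs and SAEs for 90 days after the last dose, whatever the reason for stopping, the causality, or the start of further therapy.
2. Delete the second paragraph of protocol 8.2.2 or align it with the first.
3. Remove the start of new therapy as a limit on AE collection in the Synopsis overall design, protocol 2.3 and 7.1, and SAP 2.2.1.
4. Hold the follow-up call no earlier than 90 days after the last dose. An extra call before new therapy is optional.
5. Record the start date of subsequent cancer therapy.
6. Add the 90-day end to the SAP's TEAE definition and the new-therapy flag to its AE listings, and show the AE summaries with and without flagged events.

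The cost is protocol wording, one date field, and small edits to the SAP text and shells. The call is already scheduled. The downside is that some events collected will be due to the next therapy. A flag in the listings alone would leave them in the summaries, which is why both sets of summaries are needed.
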